The Investigator must review the laboratory report, document this review, and record any clinically relevant changes occurring during the study in the AE section of the eCRF. The laboratory reports must be filed with the source documents. Clinically significant abnormal laboratory findings are those which are not associated with the underlying disease, unless judged by the Investigator to be more severe than expected for the participant's condition.

- In the event of unexplained abnormal clinically significant laboratory test values, the tests should be repeated immediately and followed up until they have returned to the normal range and/or an adequate explanation of the abnormality is found.
- If such values do not return to normal/baseline within a period of time judged reasonable by the Investigator, the etiology should be identified and the Sponsor notified.
- If laboratory values from non-protocol specified laboratory assessments performed at the local laboratory require a change in participant management or are considered clinically significant by the Investigator (e.g., SAE or AE or dose-modification) then, the results must be recorded in the eCRF.

Additional blood or urine samples may be taken at the discretion of the Investigator if the results of any test fall outside the reference ranges, or clinical symptoms necessitate additional testing to monitor participant safety.

Where the clinical significance of abnormal laboratory results at screening are considered uncertain, screening laboratory tests may be repeated before randomization to confirm eligibility.

In the event of unexplained abnormal clinically significant laboratory test values, the tests should be repeated immediately and followed up until they have returned to the normal range and/or an adequate explanation of the abnormality is found. If there is an alternative explanation for a positive blood test for drugs of abuse (e.g., previous occasional intake of a medication or food containing for example, codeine, benzodiazepines or opiates) the test could be repeated to confirm washout. Results of clinical laboratory testing will be recorded on the eCRF or be received as electronically produced laboratory reports submitted directly from the local or central laboratory.

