Potential analysis considerations for analyzing laboratory data include the use of Standard Reference Ranges and potential transformation of data for specific lab tests.

In this scenario, Roche standard reference ranges, rather than the reference ranges of the Investigator, can be used for specific parameters. For these parameters, the measured laboratory test result will be assessed directly using the Roche standard reference range. Certain laboratory parameters will be transformed to Roche's standard reference ranges.

A transformation will be performed on certain laboratory tests that lack sufficiently common procedures and have a wide range of Investigator ranges, e.g., enzyme tests that include AST, ALT, and alkaline phosphatase and total bilirubin. Since the standard reference ranges for these parameters have a lower limit of zero, only the upper limits of the ranges will be used in transforming the data.

Definition of Laboratory Abnormalities

For all laboratory parameters included in the analysis described above, there exists a Roche predefined standard reference range. Laboratory values falling outside this standard reference range will be labeled "H" for high or "L" for low in participant listings of laboratory data.

In addition to the standard reference range, a marked reference range has been predefined by Roche for these laboratory parameters. The marked reference range is broader than the standard reference range. Values falling outside the marked reference range that also represent a defined change from baseline will be considered marked laboratory abnormalities (i.e., potentially clinically relevant). If a baseline value is not available for a participant, the midpoint of the standard reference range will be used as the participant's baseline value for the purposes of determining marked laboratory abnormalities. Marked laboratory abnormalities will be labeled in the participant listings as "HH" for very high or "LL" for very low.

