1.1 OBJECTIVES AND ENDPOINTS

Table 1 Primary and Secondary Objectives

Primary Objective	Endpoint
To evaluate the efficacy of 12-week treatment with alogabat compared with placebo in treating social communication deficits in participants with Autism Spectrum Disorder (ASD)	 Change from baseline to Week 12 in the Adaptive Behavior Composite score of the Vineland[™] Adaptive Behavior Scales, Third Edition (Vineland[™]-3)
Secondary Objectives	Endpoints
To evaluate the safety and tolerability of a 12-week treatment with alogabat in 15-to 45-year-old participants with ASD	 Incidence and severity of adverse events (AEs) and serious adverse events (SAEs)

	Incidence of treatment discontinuations due to AEs Change from baseline over time and
	 Change from baseline over time and incidence of clinically relevant abnormalities in vital signs including orthostatic changes, electrocardiogram (ECG) parameters and safety laboratory values including the incidence of marked laboratory abnormalities
	 Change from baseline over time in suicide risk (using the Columbia-Suicide-Severity Rating Scale [C-SSRS])
	 Incidence of daytime sleepiness assessed with the Karolinska Sleepiness Scale (KSS), the Epworth Sleepiness Scale (ESS) or the ESS for children and adolescents (ESS- CHAD), and the Sudden Onset of Sleep Questionnaire
To evaluate the efficacy of a 12-week treatment with alogabat compared with placebo on restricted and repetitive behaviors (RRBs)	Change from baseline to Week 12 in behavior/symptoms as measured by all domains of the Repetitive Behavior Scale-Revised (RBS-R) scale
To evaluate the efficacy of a 12-week treatment with alogabat compared with placebo on social behaviors	Change from baseline to Week 12 on the Vineland-3 Socialization domain
To evaluate the efficacy of a 12-week treatment with alogabat compared with placebo on communication skills	Change from baseline to Week 12 on the Vineland-3 Communication domain

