4.1 GENERAL CONSIDERATIONS

Table 4 Analysis Time Windows

Assessments will be assigned to analysis study days according to visit windows defined below:

Analysis Window Label	Baseline	Day 1	Day 7	Day 14	Day 42	Day 63 (c)	Day 84	
Planned Study Day	1 (a)	1	1	14	42	63	84	
ECGs	ECGs							
Study Day	≤ 1 (a)	1	-	2 to 28	-	-	≥ 71	
Vital Signs,	Vital Signs, KSS							
Study Day	≤ 1 (a)	1	-	2 to 28	29 to 55	-	≥ 71	
Lab (Hematology, Chemistry, Urinalysis)								
Study Day	≤ 1 (a)	-	-	2 to 28 (b)	29 to 55	56 to 70	≥ 71	
ESS								

Study Day	≤ 1	-	-	2 to 28	29 to 70	-	≥ 71			
ESS-CHAD										
Study Day	≤ 1	-	-	2 to 28	29 to 55	56 to 70	≥ 71			
Coagulation	Coagulation									
Study Day	≤ 1 (a)	-	-	-	-	56 to 70	≥ 71			
Vineland-3, RBS-R, CRRI, BAI, PRAS-ASD, SSP, AASP, PedsQL, PROMIS, Anthropometric Measurements										
Study Day	≤ 1 (a)	-	-	-	-	-	≥ 71			
CGI-S, CGI-	l (d)									
Study Day	≤ 1 (a)	-	-	2 to 28 (b)	29 to 70	-	≥ 71			
Neurocogni	itive Battery	/								
Study Day	≤ 1 (a)	1	-	2 to 28 (b)	29 to 70	-	≥ 71			
Sudden Onset of Sleep										
Study Day	≤ 1	-	2 to 10	11 to 28	29 to 55	56 to 70	≥ 71			
(a) Latest assessment prior to intake of first study medication. Use date and time, if available.										

⁽b) May include assessments on day 1 if after the time of first study medication.

If more than one assessment is in the same time window, the assessment that is closest to the planned study day will be selected to enter the summary tables.

Table 5 General Descriptive Statistics

Continuous variables will be summarized with the following descriptive statistics and nomenclature:

n	number of observations or participants
mean	arithmetic mean
SD	standard deviation

⁽c) Planned for adolescent participants only.

⁽d) No baseline for CGI-I.

min	minimum value
q1	first quartile value
median	median value
q 3	third quartile value
max	maximum value

Categorical variables will be summarized and presented with the following nomenclature:

n	frequency
%	percentage

Percentage by category will be based on the number of participants exposed within a category. Categories of NOT REPORTED, MISSING, and/or UNKNOWN will be excluded from summaries if null or n/a.

Besides descriptive summaries, listings, and plots will be provided where deemed necessary. Listings will also include multiple assessments within the same time window.

Table 6 ADaM Datasets

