

APPENDIX 1

LIST OF PLANNED OUTPUTS FOR EFFICACY AND SAFETY

Provisional Output Name	Population	Title	
l_ae_gloss	Safety	Glossary of Adverse Event Preferred Terms and Investigator-Specified Adverse Event Terms	
I_ae	Safety	Listing of Adverse Events	
I_ae_postdose	Safety	Listing of new onset AEs after last dose of study medication	
l_ae_disc	Safety	Listing of Adverse Events Leading to Study Treatment Discontinuation	
l_cm_gloss	Safety	Glossary of Concomitant Medication Class, Preferred Name, and Investigator-Specified Terms	
I_cm	Safety	Listing of Concomitant Medication	

l_cssrs	Safety	Columbia-Suicide Severity Rating Scale (C-SSRS)	
l_ds	Safety	Listing of Patients who Discontinued from Study	
l_dv	Safety	Listing of Major Protocol Deviations	
I_eg	Safety	Listing of ECG Data	
l_ex_ti	Safety	Listing of Drug Administration and Dosing Time	
l_mh_gloss	Safety	Glossary of Medical History Coded Terms	
I_mh	Safety	Listing of Medical History	
l_vs	Safety	Listing of Vital Signs	
t_ae_int	Safety	Adverse Events by Greatest Intensity	
t_ae_oview	Safety	Safety Summary	
t_ae	Safety	Adverse Events	
t_cssrs	Safety	Columbia-Suicide Severity Rating Scale (C-SSRS)	
t_dm	Safety	Demographic and Baseline Characteristics	
t_ds	Safety	Patient Disposition	
t_eg_cfb	Safety	ECG Parameters Change from Baseline by Visit	
t_ess_cat	Safety	Epworth Sleepiness Scale (ESS) Total Score Categories	
t_ess_cfb	Safety	Epworth Sleepiness Scale (ESS) Change from Baseline by Visit	
t_ess_chad_c at	Safety	ESS for Adolescents Sleepiness Scale (ESS-CHAD) Total Score Categories	
t_ess_chad_cf b	Safety	ESS for Adolescents Sleepiness Scale (ESS-CHAD) Change from Baseline by Visit	
t_ex	Safety	Study Treatment Exposure	
t_kss_cfb	Safety	Karolinska Sleepiness Scale (KSS) Change from Baseline by Visit	
t_lb_abn_ls	Safety	Laboratory Abnormalities (Standardised parameters)	
t_lb_abn_nls	Safety	Laboratory Abnormalities (Non-Standardised parameters)	

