t_lb_cfb_ls	Safety	Laboratory Tests and Change from Baseline by Visit (Standardised parameters)	

t_lb_cfb_nls	Safety	Laboratory Tests and Change from Baseline by Visit (Non-Standardised parameters)	
t_neuro_cfb	Safety	Neurocognitive Battery Change from Baseline by Visit	
t_sudden	Safety	Sudden Onset of Sleep Questionnaire	
t_vs_cfb	Safety	Vital Signs Change from Baseline by Visit	
l_ae_ser	Safety	Listing of Serious Adverse Events	
l_dm	Safety	Listing of Demographic and Baseline Characteristics	
l_lb_abn	Safety	Listing of Laboratory Abnormalities	
I_lb	Safety	Listing of Laboratory Data and Change from Baseline by Visit	
t_ae_pt	Safety	Adverse Events by Preferred Term	
t_ae	Safety	Adverse Events Related to Study Treatment	
t_cm	Safety	Medications Started after Baseline by Medication Class and Preferred Name	
t_cm	Safety	Medications Ongoing at Baseline by Medication Class and Preferred Name	
t_cm	Safety	Medications Completed Prior to Baseline by Medication Class and Preferred Name	
t_eg_abn	Safety	ECG Parameters outside Normal Limits Regardless of Abnormality at Baseline	
t_eg_abnbl	Safety	ECG Parameters outside Normal Limits Among Patients without Abnormality at Baseline	
t_eg_qtcf	Safety	QTcF Actual Values and Change from Baseline by Visit	
t_mh	Safety	Previous and Concurrent Medical History	
I_ae_nsaesi	Safety	Listing of Non-Serious Adverse Events of Special Interest	
t_ae_nsaesi	Safety	Non-Serious Adverse Events of Special Interest	
g_ex_hist	Safety	Histogram of Dosing Time	
g_vs_mean	Safety	Mean Plot from of Vital Sign Parameters Over Time with 95% CI	
g_vs_mean_cfb	Safety	Mean Change from Baseline Plot of Vital Sign Parameters Over Time with 95% Cl	

[figure not shown]
g_lb_mean_ls	Safety	Roche-Standardized Laboratory Data
g_lb_mean_nl s	Safety	Non-Standardized Laboratory Data
g_eg_mean	Safety	Mean Plot of ECG Parameters Over Time with 95% Cl
g_eg_mean_cfb	Safety	Mean Change from Baseline Plot of ECG Parameters Over Time with 95% CI
g_ess	Safety	ESS over Time
g_ess_cfb	Safety	ESS Change from Baseline over Time
g_kss	Safety	KSS over Time
g_kss_cfb	Safety	KSS Change from Baseline over Time
g_neuro	Safety	Neurocognitive Battery

[figure not shown]
t_vabs3_ancov	Efficacy	Vineland-3 ABC GSV Score ANCOVA no interactions
t_vabs3_ancov	Efficacy	Vineland-3 ABC GSV Score ANCOVA age interaction
t_vabs3_ancov a	Efficacy	Vineland-3 ABC GSV Score ANCOVA IQ interaction
t_vabs3_ancov a	Efficacy	Vineland-3 SOC GSV Score ANCOVA no interactions

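### Read literally, the SAP's closest-day rule also feeds the laboratory and ECG abnormality tables, so an abnormal value can drop out of the incidence count

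*SAP*

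**What the plan says.** SAP 4.1 assigns assessments to the windows of Table 4. If a window contains more than one, "the assessment that is closest to the planned study day will be selected to enter the summary tables". The records not chosen go elsewhere: "Listings will also include multiple assessments within the same time window". No table type is exempted.

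The secondary safety endpoints in SAP 1.1 cover clinically relevant abnormalities in vital signs, ECG parameters and "safety laboratory values including the incidence of marked laboratory abnormalities". The tables that would report them are listed in SAP Appendix 1: t_lb_abn_ls and t_lb_abn_nls for laboratory data, and t_eg_abn and t_eg_abnbl for ECGs. The first ECG table is titled "ECG Parameters outside Normal Limits Regardless of Abnormality at Baseline". SAP 4.4 promises tabular summaries and listings, with abnormal laboratory results flagged, but does not say which records count towards incidence.

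Protocol 8.2.5 says of unexplained, clinically significant abnormal laboratory results that "the tests should be repeated immediately and followed up until they have returned to the normal range", or until an adequate explanation is found. Protocol Appendix 4 sets the definition: "Values falling outside the marked reference range that also represent a defined change from baseline will be considered marked laboratory abnormalities".

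**The concern.** A rule that picks one record per window suits a by-visit mean. It does not suit an incidence count, where the question is whether the participant ever had an abnormal value. The protocol itself generates the second record, because an unexplained, clinically significant abnormal result must be repeated. If the repeat has recovered and lies nearer the planned day, the table shows the recovered value and the abnormal one survives only in a listing, which gives no incidence by arm.

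A second route needs no repeat. In Table 4 the last laboratory and ECG window is open-ended from Day 71. The Schedule of Activities (Protocol Table 1) also collects haematology, chemistry, coagulation, urinalysis and ECGs at the 2-week follow-up. An off-treatment follow-up value can therefore stand in for an early Week 12 value. At stake is the between-arm comparison of abnormality rates in a secondary endpoint.

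**Working it through.** The plan gives no figure for this point, so there is none to reproduce. The check reads the rule against the output list and then enumerates it.

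**Inputs.** Planned Days 14, 42 and 84, with laboratory windows of Days 2–28, 29–55 and Day 71 onwards (SAP Table 4). ECGs share the first and last of these. Visit windows are ±7 days, and the 2-week follow-up is at the Week 12 visit + 14 days, ±7 (Protocol Table 1). *Assumed, not in the documents:* each of the 15 day offsets is equally likely, and one normal repeat follows.

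**1. A single case.** Abnormal ALT on Day 38, normal repeat on Day 41, planned Day 42. Both fall in the Day 29–55 window. The distances are |38 − 42| = 4 and |41 − 42| = 1, so the normal value is selected.

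**2. How often a normal repeat displaces the abnormal value.** Let the visit fall d days from plan and the repeat r days after the visit. Displacement needs |d + r| < |d|, that is d < −r/2.

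| Gap r (days) | Offsets d that give displacement | Share of 15 |
|---|---|---|
| 1 | −7 to −1 | 7/15 = 47% |
| 2 | −7 to −2 (tie at −1) | 6/15 = 40% |
| 3 | −7 to −2 | 6/15 = 40% |
| 5 | −7 to −3 | 5/15 = 33% |
| 7 | −7 to −4 | 4/15 = 27% |

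A visit on or after the planned day never loses its abnormal value this way. A same-day repeat is always a tie, which the rule leaves unresolved and which is not counted here.

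**3. Follow-up displacing Week 12.** Let Week 12 fall at Day 84 + d and follow-up at Day 84 + d + 14 + u, with u from −7 to +7. Follow-up is selected if |d + 14 + u| < |d|. That happens for 7 values of u at d = −7, 5 at d = −6, 3 at d = −5 and 1 at d = −4. The total is 16 of 15 × 15 = 225 combinations (7.1%), with 4 further ties. For example, with Week 12 on Day 77, a follow-up on Days 84 to 90 replaces it.

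**4. Effect on participant incidence, as an illustration only.** Suppose three on-treatment laboratory visits, a 5% chance of an abnormal value at each, and every abnormal value repeated and normal. Counting all values gives 1 − 0.95³ = 14.3%. With a displaced share of 4/15, the result is 1 − (1 − 0.05 × 11/15)³ = 10.6%. With 7/15, it is 1 − (1 − 0.05 × 8/15)³ = 7.8%. The 5% is invented, and repeating every abnormal value goes beyond what the protocol requires.

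**The case against.** The strongest reply is that the rule was never meant for these tables. It sits under a table of analysis visits. Appendix 1 labels the laboratory and ECG change-from-baseline tables as by visit and leaves that label off all four abnormality tables. The ECG pair is split by baseline status, which fits a count of any post-baseline abnormality per participant. Protocol Appendix 4 defines a marked abnormality value by value, with no window selection. Under that reading the under-count is zero. This stands as a plausible intention, but no sentence in the SAP states it, and the only written selection rule says otherwise. SAP 4.1.2 mentions unscheduled and repeated measurements for baseline, but there is no matching rule after baseline. The sponsor standards invoked in SAP section 5 concern output layout.

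Other parts of the reply also stand:

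- The mandatory repeat covers only unexplained, clinically significant laboratory values, and early repeats may still be abnormal.
- Values of that kind are reportable as adverse events (Protocol Appendix 3, section 4) and so reach the AE tables.
- ALT or AST elevation with raised bilirubin or jaundice, and confirmed QTcF above 480 ms or a rise above 60 ms, are special-interest events with their own table (t_ae_nsaesi).
- The repeat route is weak for ECGs. Repeats are optional, to rule out lead misplacement (Protocol 8.2.4), and QTcF confirmation is within 30 minutes (Protocol 4.1.2), hence normally a same-day tie. Only the follow-up route clearly affects ECGs.

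A reader might infer that liver or QTcF signals would be lost. The documents do not support that, because the defined events are captured separately.

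**Conclusion.** The rule is unqualified, the abnormality outputs are summary tables, and no any-post-baseline or worst-value rule appears in SAP 4.1, 4.4 or Appendix 1. Followed as written, the plan can under-count laboratory abnormalities and can let an off-treatment laboratory or ECG value replace an early Week 12 value. It is tempting to say that the endpoint is under-counted. That goes too far, because it depends on the literal reading, on an early visit and on the later value being normal.

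The exposure is mainly isolated laboratory abnormalities and ECG findings below the special-interest thresholds. The 27% to 47% applies only to abnormal values followed by a normal repeat 1 to 7 days later, under uniform visit timing. Even then 53% to 73% are not displaced, and a participant with a retained abnormal value in another window is still counted. The number of participants affected cannot be derived from the documents.

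**What to change.** In SAP 4.1, limit the closest-day rule to by-visit summaries and plots. State that t_lb_abn_ls, t_lb_abn_nls, t_eg_abn and t_eg_abnbl classify each participant by the worst valid post-baseline value, including unscheduled and repeat records but excluding technically invalid ECG tracings. Define the on-treatment period for these tables and give its end, so that the open-ended last window no longer mixes Week 12 with follow-up.

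If an any-post-baseline count was intended all along, the same text simply confirms it. The cost is about a sentence in the SAP and an analysis flag in the laboratory and ECG datasets, with no new data. Reported incidence may come out slightly higher than under the literal rule.

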4.1.2 Baseline Definitions

Unless otherwise stated, baseline is defined as the last observation recorded before the first study drug administration. The last observation can be an unscheduled / repeated measurement. If a pre-treatment observation is missing, then the pre-baseline (preferred) or screening value may be used.

As the age at screening was determining the choice of questionnaires, and for reasons of consistency, the age at screening was chosen to be the analysis age.

ECG baseline is defined as the mean of the triplicate measurement before the first study drug administration on Day 1.

4.1.3 Characteristics of Efficacy Endpoints

Vineland-3

The Vineland-3 (Sparrow et al. 2016) is a semi-structured interview that measures an individual's adaptive behaviour across three domains of communication, socialisation and daily living skills. Additional domains of motor skills (only used in children up to 9 years of age) and maladaptive behaviours were not captured in this study. Each adaptive behaviour domain is composed of three subdomains. Subdomain raw scores are used to derive two types of scores: Standard (V-scale scores; range from 1-24) and Growth Scale Values (GSVs). Standard scores are scores relative to a normative age group and can range from 20-140. A GSV is a person-ability score that is used to track an individual's progress. A higher score indicates better adaptive functioning.

Repetitive Behaviour Scale-Revised (RBS-R)

The RBS-R (Bodfish, 1999) is a 43-item informant-based questionnaire, assessing the variety of restricted and repetitive behaviours observed in individuals with ASD. A total RBS-R score is calculated as the sum of the scores for the 43 items. The total RBS-R score ranges from 0 to 129, with a higher score indicating more severe repetitive and restrictive behaviours. The RBS-R subscale scores will also be calculated as the sum of the scores for each item within each subscale.

Caregiver-Reported Routines Inventory (CRRI)

The CRRI is a 62-item caregiver-reported restricted and repetitive behaviours scale for older adolescents and adults based on the Children Routine Inventory-Revised (CRI-R; Evans et al 2017). It has been developed by the author in collaboration with the Sponsor in order to extend the age-range to older adults and adolescents. The CRRI questionnaire captures a wide range of restrictive and repetitive behaviours, including stereotypies, tics, compulsions, habits, sensory sensitivities, and focused interests, in the context of typical and atypical development in adults and adolescents. A total score is calculated as the sum of the scores for the 62 items. The scores range from 62 to 310, with a higher score indicating more severe repetitive and restricted behaviours. The CRRI subscale scores will also be calculated as the sum of the scores for each item within each subscale.

Clinical Global Impression-Severity (CGI-S) and Improvement (CGI-I) Scales

The CGI rating scales are tools used to evaluate both the severity of illness and change from Baseline (Guy et al 1976). The CGI-S reflects the rater's impression of the participant's current autism severity on a 7-point scale ranging from no symptoms (1) to very severe symptoms (7). The CGI-I is used to assess the clinical change as compared with symptoms at baseline using a 7-point scale, ranging from very much improved (1) to very much worse (7). For this study, modified versions will be used (Busner and Targum 2007).

Beck Anxiety Inventory (BAI)

The BAI is a well-validated 21-item participant-administered inventory probing for common symptoms of anxiety (Beck et al 1988). Each item contains four possible responses, which range in severity from 0=not at all (e.g., unable to relax) to 3=severely (e.g., it bothered me a lot). Participants are asked to provide answers based on the way they have been feeling over the past month, including the assessment day. A total score is calculated as the sum of the score for the 21 items. The scores range from 0 to 63, with a higher score indicating greater levels of anxiety.

Parent-Rated Anxiety Scale-ASD (PRAS-ASD)

The PRAS-ASD is a support person-rated scale with 25 items to assess the severity of anxiety symptoms in children and adolescents with ASD. Support persons of adolescent participants will be asked to describe their child's worries and anxiety-related behaviors over the past 2 weeks on a 0 to 3-point scale from "NONE=not present", "MILD=present sometimes, not a real problem", "MODERATE=often present and a problem", and "SEVERE=very frequent and a major problem". The PRAS-ASD total score is calculated

as the sum of the scores for the 25 items. The scores range from 0 to 75, with a higher score indicating greater levels of anxiety.

Short Sensory Profile 2 (SSP-2)

The Short Sensory Profile Version 2 (SSP-2; Dunn 2014) is a 34-item parent or support person-reported questionnaire that probes for the effect of sensory processing anomalies on a person's ability to function in daily life. Item responses occur on a five-point Likert-rating scale from 1 (almost never) to 5 (almost always). The SSP-2 was based on the Sensory Processing Framework (Dunn 1999) and provides scores in four quadrants based on the child's neurological threshold to sensory input and their method of self-regulation. Raw score totals are calculated for each of the four quadrants: Seeking ("the degree to which a child obtains sensory input"), Avoiding ("the degree to which a child detects sensory input."), and Registration ("the degree to which a child misses sensory input."). A Sensory raw score and Behavioral raw score will also be calculated. The score ranges from 0 to 100 (depending on the subscale), with a higher score indicating more frequent sensory behaviors and symptoms.

Adolescent/Adult Sensory Profile (AASP)

The Adolescent/Adult Sensory Profile (Brown and Dunn 2002) is a self-reported questionnaire consisting of 60 items rated for frequency of the behavior at home or in the community. Raw score totals are calculated for each of the four quadrants: "Low Registration", "Sensation Seeking", "Sensory Sensitivity", and "Sensation Avoiding". The raw scores for each quadrant range from 15 to 75, with higher scores indicating more frequent sensory behaviors and symptoms.

Patient-Reported Outcomes Measurements Information System (PROMIS)

The Patient-Reported Outcomes Measurements Information System (PROMIS) Sleep Disturbance Short Form (Yu Lan et al 2011, Buysse et al 2010) assesses self-reported perceptions of sleep quality, sleep depth, and restoration associated with sleep. This includes perceived difficulties and concerns with getting to sleep or staying asleep, as well as perceptions of the adequacy of and satisfaction with sleep. This questionnaire assesses sleep disturbance over the past seven days. The following versions of the Sleep Disturbance short form (8 items) will be implemented in this study: adult self-report (ages 18+, high-functioning), pediatric self-report (adolescents aged 15 to -17 years, high-functioning). In addition, proxy forms completed by the support person will be used for all adolescents, as well as low-functioning adults.

The sleep disturbance total raw score is calculated as the sum of the scores for the 8 items. The score will range from 8 to 40, with a higher score indicating greater sleep disturbance.

The PROMIS Sleep-Related Impairment Short-Form (Buysse et al 2010) assesses self-reported perceptions of waking alertness, sleepiness and function within the context of overall sleep-wake function. This questionnaire assesses sleep-related impairment over the past seven days. The following versions of the PROMIS Sleep-Related Impairment Short Form (8 items) will be implemented in this study: adult self-report (ages 18+, high-functioning), pediatric self-report (ages 15 to 17, high-functioning) and for support

persons serving as proxy reporters for the participants (adolescents aged 15 to 17 years and low-functioning adults).

The sleep-related impairment total raw score is calculated as the sum of the scores for the 8 items. The score will range from 8 to 40, with a higher score indicating greater sleep impairment.

